### 3.3.5 Cardiovascular Toxicity

Cardiovascular adverse events have been seen in subjects receiving trametinib and dabrafenib, either as monotherapy or in combination. Dose modification of either agent may be required for decreased LVEF, hypertension or QTc prolongation.

### 3.3.6 Decreased Left Ventricular Ejection Fraction (LVEF)

Decreases of the left-ventricular-ejection-fraction (LVEF) have been observed in subjects receiving trametinib monotherapy and with trametinib in combination with dabrafenib.

Therefore, a baseline echocardiogram will be performed to assess for adequate LVEF function. Repeat echocardiograms will be performed every 3 months during the duration of dabrafenib and trametinib therapy or at any point if patients develop heart failure symptoms. Management will be per the guidelines in Table 8.

**TABLE 8 DOSE MODIFICATION GUIDELINES AND STOPPING CRITERIA FOR LVEF DECREASE**

Clinic	LVEF-drop (%) or CTCAE grade	Action and Dose Modification
Symptomatic a	Grade 3: resting LVEF 39-20% or >20% absolute reduction from baseline	
 
Permanently discontinue trametinib.
 
Consult with cardiologist
 
Repeat ECHO after 2, 4, 8, 12, and 16 weeks or until resolution
 

	Grade 4: resting LVEF <20%	

Abbreviations: CTCAE = Common Terminology Criteria for Adverse Events; ECHO = echocardiogram; LLN = lower limit of normal; LVEF

= left ventricular ejection fraction;

- a. Symptoms may include: dyspnea, orthopnea, and other signs and symptoms of pulmonary congestion and edema.

### 3.3.7 Hypertension

Any level of hypertension should be actively managed. Trametinib does not need to be interrupted while mild hypertension is brought under control; however, treatment interruption and dose-reduction are recommended for more severe or symptomatic hypertension (e.g. persistent systolic blood pressure (SBP)  $\geq 160$  mmHg or diastolic blood pressure (DBP)  $\geq 100$  mmHg despite antihypertensive treatment).

### 3.3.8 QTc Prolongation

Guidelines for dose modification and stopping criteria due to QTc-prolongation are provided in Table 9 below:

**TABLE 9 WITHHOLDING AND STOPPING CRITERIA FOR QTc-PROLONGATION**

QTc-Prolongation a	Action and Dose Modification
• QTcB $\geq 501$ msec	
 
• Interrupt all study treatments until QTcB prolongation resolves to grade 1 or baseline
 
• Recommend Testing serum potassium, calcium, phosphorus and magnesium. If abnormal, correct per routine clinical practice to within normal limits.
 
• Review concomitant medication usage for a prolonged QTc.
 
• Restart at current dose level
 
• If event recurs, permanently discontinue study treatments
 

Abbreviations: msec = milliseconds; QTcB = QT interval on electrocardiogram corrected using the Bazett's formula a: Based on average QTc value of triplicate ECGs. For example, if an ECG demonstrates a prolonged QT interval, obtain two or more ECGs over a brief period, and then use the averaged QTc values of the three ECGs to determine if study treatments should be interrupted or discontinued. If the QTc prolongation resolves to grade 1 or baseline, the subject may resume study treatment if the investigator agrees.

### 3.3.9 CUTANEOUS SQUAMOUS CELL CARCINOMA (cuSCC) AND KERATOACANTHOMA (KA)

Both cuSCC and KA have been observed in subjects treated with dabrafenib and the combination of dabrafenib and trametinib [GlaxoSmithKline Document Number

Version 01 – 2019-0906

2011N126811\_00, GlaxoSmithKline Document Number 2012N136095\_00, and GlaxoSmithKline Document Number HM2009/00151/02]. These should be surgically removed according to institutional practices. Dose modification or interruption of study treatment is not required for cuSCC or KA, however they should be reported as an SAE (refer to Section 7.7).

### **3.4 MONITORING, INTERRUPTION, AND STOPPING CRITERIA FOR HEPATOBILIARY EVENTS**

These liver chemistry stopping and follow up criteria have been designed to assure subject safety and evaluate liver event etiology in alignment with the FDA Guidance for Industry – Drug-Induced Liver Injury: Premarketing Clinical Evaluation (July 2009, [www.fda.gov](http://www.fda.gov)).

Liver chemistry stopping criteria 1-5 are defined as follows:

$ALT \geq 3 \times ULN$  and  $bilirubin \geq 2 \times ULN$  ( $>35\%$  direct bilirubin) (or  $ALT \geq 3 \times ULN$  and  $INR > 1.5$ , if INR measured)

**NOTE:** If serum bilirubin fractionation is not immediately available and if  $ALT \geq 3 \times ULN$  and  $bilirubin \geq 2 \times ULN$ , subject should be discontinued from study treatments. Serum bilirubin fractionation should be performed if testing is available.

$ALT \geq 8 \times ULN$ ;  $ALT \geq 5 \times ULN$  but  $< 8 \times ULN$  persists for  $\geq 2$  weeks;  $ALT \geq 3 \times ULN$  if associated with symptoms (new or worsening) believed to be related to hepatitis (such as fatigue, nausea, vomiting, right upper quadrant pain or tenderness, or jaundice) or hypersensitivity (such as fever, rash or eosinophilia).

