**Table 1: Organ function criteria**

Hematological	
Absolute neutrophil count (ANC)	$\geq 1500/\mu L$
Platelets	$\geq 100\,000/\mu L$
Hemoglobin	$\geq 9.0\text{ g/dL}$ or $\geq 5.6\text{ mmol/L}^a$
Renal	
Creatinine OR Measured or calculated b creatinine clearance (GFR can also be used in place of creatinine or CrCl)	$\leq 1.5 \times \text{ULN}$ OR $\geq 30\text{ mL/min}$ for participant with creatinine levels $> 1.5 \times$ institutional ULN
Hepatic	
Total bilirubin	$\leq 1.5 \times \text{ULN}$ OR direct bilirubin $\leq \text{ULN}$ for participants with total bilirubin levels $> 1.5 \times \text{ULN}$
AST (SGOT) and ALT (SGPT)	$\leq 2.5 \times \text{ULN}$
Coagulation	
International normalized ratio (INR) OR prothrombin time (PT) Activated partial thromboplastin time (aPTT)	$\leq 1.5 \times \text{ULN}$ unless participant is receiving anticoagulant therapy as long as PT or aPTT is within therapeutic range of intended use of anticoagulants
ALT (SGPT)=alanine aminotransferase (serum glutamic pyruvic transaminase); AST (SGOT)=aspartate aminotransferase (serum glutamic oxaloacetic transaminase); GFR=glomerular filtration rate; ULN=upper limit of normal.	
a Criteria must be met without erythropoietin dependency and without packed red blood cell (pRBC) transfusion within last 2 weeks.	
b Creatinine clearance (CrCl) should be calculated per institutional standard.	

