**Table 5 Dose Modification Guidelines – General**

CTCAE Grade	Action and Dose Modification
Grade 1 or Grade 2 (tolerable)	Continue study treatments at same dose level (no dose modification)
Grade 2 (Intolerable)	
1 st or 2 nd occurrence	Interrupt study treatments until toxicity resolves to $\leq$ grade 1 then restart at same dose level
3 rd or occurrence	Interrupt study treatments until toxicity resolves to $\leq$ grade 1 then restart at next lower dose level
4 th or greater occurrence	Interrupt study treatments until toxicity resolves to $\leq$ grade 1 then restart at two dose levels lower than the starting dose or discontinue treatments per investigator discretion
Grade 3	
1 st occurrence	Interrupt study treatments until toxicity resolves to $\leq$ grade 1 or baseline then restart at next lower dose level
2 nd occurrence	Interrupt study treatments until toxicity resolves to $\leq$ grade 1 or baseline then restart at two dose levels lower than the starting dose
3 rd occurrence	Discontinue treatments.
Grade 4	
1 st occurrence	Discontinue treatments

For dabrafenib and/or trametinib related adverse events: if following an interruption of dabrafenib and trametinib, an AE doesn't recover to  $\leq$  Grade 1 or baseline within 4 weeks, dabrafenib and trametinib must be discontinued.

No dose reductions are allowed for spartalizumab. Dose interruption for spartalizumab includes delaying or withholding the treatment for any reason as well as an interruption of treatment during an infusion. All dose interruptions and the reason for the dose interruption must be recorded. Dose interruption for spartalizumab includes delaying or withholding the treatment for any reason as well as an interruption of treatment during an infusion. Subjects with adverse events suspected to be related to spartalizumab including those of potential immune-mediated etiology (irAE) must be permanently discontinued from spartalizumab if (1) the AE doesn't recover to  $\leq$  Grade 1 or baseline within 12 weeks and/or (2) the dose of steroids (for the management of irAE) remains  $> 10$  mg/day prednisone or equivalent for  $> 12$  weeks. The 12 week timeframe will begin from the time the irAE reaches a grade that leads to spartalizumab interruption.

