**Table 6: Pyrexia Management Guidelines**

Pyrexia		
Occurrence	Recommended adverse event management guidelines	Mandatory dose modification requirements
1 st occurrence and subsequent occurrences c	
 
• Educate patient about pyrexia syndrome and to immediately interrupt dabrafenib and trametinib at the very first symptom of pyrexia or its associated prodrome (chills, rigors, night sweats or flu-like symptoms).
 
• Clinical evaluation for infection and hypersensitivity a
 
• Laboratory work-up a
 
	
 
• Dabrafenib and trametinib must be interrupted promptly at the very first symptom of pyrexia or its associated prodrome (chills, rigors, night sweats or flu-like symptoms) and should be restarted upon improvement of symptoms at the same dose if symptom free at least 24 hours.
 
• If pyrexia cannot be managed with interruption, dose reduction per
 

Pyrexia	Occurrence	Recommended adverse event management guidelines
		
 
Administer anti-pyretic treatment with non-steroidal anti-inflammatory drugs (NSAID) and/or paracetamol b
 
Recommend oral corticosteroids (i.e., prednisone 10 mg) for at least 5 days or as clinically indicated.
 
Optimize oral corticosteroid dose as clinically indicated for recalcitrant pyrexia.
 
Oral hydration should be encouraged in subjects without evidence of dehydration. Intravenous hydration is recommended in subjects experiencing pyrexia complicated by dehydration/hypotension.
 

a For subjects experiencing pyrexia, a clinical evaluation and laboratory work-up is mandatory for each event; thorough clinical examination for signs and symptoms of infection or hypersensitivity is required; laboratory work-up should include full-blood-count, electrolytes, creatinine, blood urea nitrogen (BUN), C-reactive protein (CRP), liver-function tests, blood culture, and urine culture.

b Anti-pyretic treatment should be started immediately at the first occurrence and prophylactic anti-pyretic treatment is recommended. Anti-pyretic treatment may include acetaminophen, ibuprofen, or suitable anti-pyretic medication according to institutional standards. Prophylactic anti-pyretic treatment is recommended to be discontinued after three days in the absence of pyrexia.

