Grade 2:  AST or ALT $> 3 \times \text{ULN}$ to $\leq 5.0 \times \text{ULN}$ ; or if baseline abnormal $> 3.0 - 5.0 \times \text{baseline}$  or bilirubin $> 1.5 \times \text{ULN}$ to $\leq 3 \times \text{ULN}$ ; or if baseline abnormal $> 1.5 - 3.0 \times \text{baseline}$  (if patient meets criteria for Hy's law refer to	
 
Monitor hepatic laboratory tests more frequently (every 2-3 days) until returned to baseline values
 
Rule-out alternative causes (e.g. concomitant medications, infection, disease progression)
 
Consider prednisone (0.5-1 mg/kg/d) if liver tests worsen and/or significant symptoms
 

Grade 3 or 4: AST or ALT $> 5.0 \times \text{ULN}$ ; or if baseline abnormal $> 5.0 \times \text{baseline}$ .  bilirubin $> 3.0 \times \text{ULN}$ ; or if baseline abnormal $> 3.0 \times \text{baseline}$ .	
 
Monitor hepatic laboratory tests more frequently (every 2-3 days) until returned to baseline values.
 
Consider viral serology (i.e. hepatitis A/B/C, CMV, and rule out other potential cause of liver injury such as concomitant medications or alcohol), consultation with hepatologist and liver biopsy to establish etiology of hepatic injury
 
If after 2-3 days new liver assessment shows worsening of laboratory test consider to initiate treatment with steroids prednisone 1-2 mg/kg/day or i.v. equivalents.
 
Add prophylactic antibiotics for opportunistic infections as appropriate
 
When symptoms/liver tests improve to grade <math>\leq 1</math>, taper steroids over at least 4 weeks.
 
If serum transaminase levels or bilirubin do not decrease 48-72 hours after initiation of systemic steroids, oral mycophenolate mofetil 500 mg every 12 hours may be given as per institutional guidelines.
 
Infliximab is not recommended due to its potential for hepatotoxicity
 

Recommended clinical management for suspected immune-related rash and other skin events

Rash and other skin Events (NCI-CTCAE v5)	
Grade	Recommended management

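### The liver stopping criteria in Section 3.4 contradict the grade-based actions in Table 5, and no passage says which governs

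*Combined protocol and SAP*

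**What the plan says.** Section 3.4 introduces its list with "Liver chemistry stopping criteria 1-5 are defined as follows". The list covers:

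- ALT ≥3×ULN together with bilirubin ≥2×ULN or, where measured, INR >1.5;
- ALT ≥8×ULN;
- ALT from 5 to below 8×ULN persisting for two weeks or more;
- ALT ≥3×ULN "if associated with symptoms (new or worsening) believed to be related to hepatitis (such as fatigue, nausea, vomiting" and similar, "or hypersensitivity (such as fever, rash or eosinophilia".

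The only action it spells out is in the note on ALT plus bilirubin without fractionation: "subject should be discontinued from study treatments".

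Table 5, labelled general, assigns actions by CTCAE grade. Grade 1 and tolerable Grade 2 need no change. Intolerable Grade 2 is paused and restarted. A first Grade 3 event is paused until it falls to "grade 1 or baseline then restart at next lower dose level", and a second restarts two levels below the starting dose. A third Grade 3 event, or any Grade 4, ends treatment. Section 3.3.2 gives 21 days for recovery. After that, withdrawal is recommended, but the investigator may continue at a reduced dose. The text under Table 5 gives four weeks, after which dabrafenib and trametinib must end.

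The ALT ranges belonging to these grades are printed only in the Appendix B liver table. It cites CTCAE version 5, the version that Section 5.2 adopts. Grade 2 is above 3 and up to 5×ULN, and Grades 3 and 4 share one row above 5×ULN. If baseline is abnormal, the same multiples apply to baseline. Table 1 admits AST and ALT up to 2.5×ULN.

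Three other passages touch the same patients. The Appendix B liver table advises staff to "Monitor hepatic laboratory tests more frequently (every 2-3 days) until returned to baseline values", and adds work-up and steroids. Table 6 says that dabrafenib and trametinib, once interrupted for pyrexia, "should be restarted upon improvement of symptoms at the same dose if symptom free at least 24 hours". Section 3.7 allows spartalizumab to restart once prednisone has been tapered to 10 mg/day.

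**The concern.** Section 3.4 works on ULN multiples, duration and symptoms, and Table 5 works on grade and tolerability. The two systems overlap on ALT, and the protocol nowhere says which prevails. A site that follows Table 5 as written can keep a patient on drug who meets a stopping criterion. A site that follows Section 3.4 can end treatment in a patient for whom Table 5 prescribes continuation or restart.

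This is first a safety matter. It also bears on how uniformly the triplet is delivered, because the primary objective concerns the 12-month RFS rate in non-pCR patients on that regimen. The sample size rests on 24 such patients, so one patient handled differently is 1/24, or about 4%, of the group. The documents do not allow the effect on RFS to be quantified.

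**Working it through.** The plan states no figure to reproduce. The check maps each ALT result to Section 3.4, then to a grade by the Appendix B ranges, then to the Table 5 action.

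**Inputs.** The ALT criteria come from Section 3.4, the grade ranges from the Appendix B liver table, the actions from Table 5, the recovery windows from Section 3.3.2 and the text under Table 5, and the entry ceiling of 2.5×ULN from Table 1.

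| Case | Section 3.4 | Grade by Appendix B | Table 5 |
|---|---|---|---|
| A. Normal baseline, ALT 4×ULN, tolerable new fatigue believed due to hepatitis | Criterion met (≥3×ULN with symptoms) | 2 | Continue, same dose |
| B. Baseline 2.5×ULN, ALT 7×ULN for two weeks | Criterion met (5 to <8×ULN, ≥2 weeks) | Below 2 | Continue, same dose |
| C. Normal baseline, ALT 6×ULN for two weeks | Criterion met (same) | 3 or 4 | If 3: pause, restart lower. If 4: discontinue |
| D. Normal baseline, ALT ≥8×ULN | Criterion met | 3 or 4 | If 3: pause, restart lower. If 4: discontinue |

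**Case A.** Even if stopping means only a pause, one passage halts drug and the other continues it.

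**Case B.** For an abnormal baseline, Grade 2 starts above 3 × baseline.
- 3 × 2.5 = 7.5×ULN.
- 7 / 2.5 = 2.8 times baseline, which is below Grade 2.
- In general, with baseline b in ULN units, an ALT of 5×ULN is at or below 3b once b ≥ 5/3 = 1.67.
- So for entry values from 1.67 to 2.5×ULN, a persistent ALT between 5×ULN and 3b meets the Section 3.4 criterion while grading below 2. At the ceiling this band runs from 5 to 7.5×ULN.

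Again the conflict does not depend on whether stopping is permanent.

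**Case C.** Assume that drug is paused on the day ALT first enters the range. The Section 3.4 criterion is met on day 14. At that point 21 − 14 = 7 days remain in the Section 3.3.2 window and 28 − 14 = 14 days in the window under Table 5. Recovery in that time leads to restart under the grade-based rules. If stopping in Section 3.4 is permanent, the passages conflict. If it means a pause, they agree.

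**Case D.** The same reasoning applies where the value is graded 3. The documents do not print the cut-point between Grades 3 and 4, so the upper end of the conflict cannot be located from them.

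**Undefined action.** Outside the ALT-plus-bilirubin note, Section 3.4 does not say whether stopping is permanent or which drugs it covers. Its title mentions interruption, but no interruption or restart rule follows.

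**The case against.** The best defence is structural. Table 5 is titled general, and Tables 6 to 9 are event-specific and depart from it. Table 9, for instance, restarts at the current dose level. On that pattern Section 3.4 is the liver-specific rule and overrides Table 5. This is a reasonable reading, but it is written nowhere. It would also leave a gap, because Section 3.4 gives an instruction for only one of its criteria, and a site looking for the action would return to Table 5.

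A second defence is that stopping may include interruption. That removes Case C, and Case D where it is graded 3, but not Cases A and B.

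A reader might infer a wider conflict, in which Appendix B and Table 6 also tell sites to continue or restart where Section 3.4 stops. The documents do not support that.

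- The Appendix B liver table says nothing about study drug in its readable text, and silence is not an instruction to continue. Where the appendix means continue, as for a Grade 1 infusion reaction, it says so. Section 3.5 says that severe or persistent immune-related events typically call for interruption or permanent discontinuation. The liver table's reference for Hy's law cases is cut off in the text available, so no argument should rest on it.
- Table 6 covers pyrexia suspected to be due to dabrafenib or trametinib. Its footnote requires a hypersensitivity examination and liver tests at every episode, so it can be applied in sequence with Section 3.4. The two overlap only when fever with ALT ≥3×ULN is judged to reflect hypersensitivity, or the event is judged to be hepatitis.

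Two further inferences also fail. A 20% rise from the entry ceiling (3 / 2.5 = 1.2) triggers nothing in Section 3.4 without symptoms, bilirubin or INR. And frequent pyrexia says nothing about how often pyrexia comes with raised ALT. The documents give no ALT rate.

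**Conclusion.** The contradiction between Section 3.4 and Table 5 is real. It is firm for ALT above 3 and up to 5×ULN with tolerable qualifying symptoms. It is also firm for persistent ALT of 5×ULN or more in patients whose abnormal entry value keeps them below Grade 2. It is conditional for Grade 3 values, where it depends on stopping being permanent. Because it sits in a safety rule, the passages must be reconciled.

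Table 6, Section 3.7 and the Appendix B liver table do not directly contradict Section 3.4. Their readable text simply gives no link to its criteria, so staff working from those pages are not sent to it.

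The conclusion assumes that the Appendix B ranges, including the baseline rule, supply the grade used in Table 5. They are the only ALT grade ranges printed. The number of patients affected cannot be estimated from the documents. Sample size and power are unaffected, and no view is taken on which clinical rule is right.

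**What to change.** Amend the text so that:

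1. Section 3.4 is reconciled with Section 3.3.2 and with Table 5 and the text beneath it, including the 21-day and four-week windows.
2. One sentence states which passage governs a liver event.
3. Each Section 3.4 criterion is marked as interruption or permanent discontinuation, and the drugs it covers are named.
4. The ALT reference, ULN or baseline, is stated for patients who enter with an abnormal value.
5. Table 6, Section 3.7 and the Appendix B liver table each carry a cross-reference to Section 3.4. The rule need not be repeated in each place.

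The clinical team chooses the content of the rule. The cost is one protocol amendment to existing text and tables, with no new tests or visits.

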### **3.5 Adverse events of special interest (AESI)**

Adverse events of special interest include AEs of a potential irAE that are associated with spartalizumab treatment. An irAE may be experienced by subjects treated with spartalizumab due to its mechanism of action and predicted based on the reported experience with other immunotherapies that have a similar mechanism of action. Investigators must be vigilant and carefully identify AEs that may be suggestive of potential irAEs as their appearance may be sub-clinical and early diagnosis is critical for its adequate management and resolution.

An irAE is typically low grade and self-limited, often occurring after multiple doses, and most frequently involving the GI tract (diarrhea/colitis), skin (rashes), liver (hepatitis), lung (pneumonitis), kidneys (nephritis) and endocrine systems (a variety of endocrinopathies) and rarely CNS (encephalitis). Serological, immunological and histological assessments should be performed as deemed appropriate by the investigator, to verify the potential immune-related nature of the AE, and exclude a neoplastic, infectious or metabolic origin of the AE.

Severe grade or persistent lower grade irAEs typically require interrupting or permanently discontinuing treatment and administration of systemic steroids or other non-corticosteroid immunosuppressive medication when systemic steroids are not effective. Early recognition of irAEs and initiation of treatment are critical to reduce the risk of complications, since the majority of irAEs are reversible with the use of steroids and other immune suppressants.

In some cases, it may be unclear to determine if an adverse event is immune related or not, thus the following dose reduction guidelines should be followed.

The following sections address the specific instructions for mandatory dose modifications and recommended management for AEs considered suspected to be related to study treatment. For subjects who do not tolerate the protocol-specified dosing schedule, dose interruptions or modifications are mandated in order to allow subjects to continue study treatment.

